#### **Rituximab**

Infusion reactions (within 24 hours of the infusion) may occur in up to 50% of patients receiving rituximab. Pre-medication with 100 mg IV methylprednisolone will be administered prior the first infusion to minimise the effect of such reactions. Sites will follow local pre-medication practice for infusions 2, 3, and 4. 100 mg IV methylprednisolone will be administered prior to each maintenance dose. Symptoms include – fever, chills, rigors, urticaria/rash, pruritis, flushing, angioedema, nausea, vomiting, fatigue, headache, rhinitis, throat irritation, bronchospasm and hypotension. However, lower rates were observed in the two randomised controlled induction trials. In the RITUXVAS study, 2/33 patients experienced an infusion reaction and in RAVE, only 1/99 experienced an infusion reaction severe enough to prevent administration of further infusions of rituximab.

Infusion reactions – fever, chills, rash, pruritis, flushing, throat irritation, angioedema, nausea and vomiting, fatigue, headache, hypotension and bronchospasm.

Mild infusion reactions are common, and can be treated by stopping the infusion, and restarting at a lower rate, together with antihistamine, antiemetic and paracetamol.

Severe infusion reactions have occurred but are rare. Hydrocortisone and adrenaline should be available for administration if needed (as per hospital protocol). Following a moderate or severe infusion reaction, patients should be

admitted to hospital for observation.

Following treatment, bone marrow suppression including leucopaenia and neutropaenia can occur. Following rituximab treatment, severe skin reactions such as TEN (Toxic epidermal necrolysis) and SJS (Stevens Johnson Syndrome) have been reported very rarely (see section 11.1.5). Infusion reactions, skin reactions, leucopaenia and neutropaenia do not require reporting, unless they meet the criteria for a serious adverse event (SAE) – see section 13.1.4 for definition of SAE.

Infections can also occur, including very rarely, reactivation of hepatitis B, and progressive multifocal leucoencephalopathy caused by reactivation of the JC virus. All infections are being collected as adverse events of interest. See section 13.4.

If discontinuation of rituximab is being considered for any reason, then the TMC must be consulted.

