### 5.2.2 Secondary endpoints

1. Proportion of patients who maintain remission at 24 and 48 months.
2. Time to a major or second minor relapse.
3. Cumulative accrual of damage as measured by the combined damage assessment score (CDA).
4. Health-related quality of life as measured using SF-36.
5. Cumulative GC exposure.
6. Severe adverse event rate.
7. Infection (treated with intravenous or oral antibiotics) rates.

 Time measured from enrolment.

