## 5. Treatment Exposure (Treatment Form)

---

 A different scoring system from the one used in the Induction phase report is employed. This new scoring system is based on COMBIVAS's VDI (Vasculitis Damage Index) form. The new scoring system has a maximum score of 64, compared to the Induction phase report one that had a maximum score of 110. For comparison new CDA scores for the Induction phase months (visits Month 0 and Month 4) will be included in this report. Further details on how the CDA score is computed can be found in section 9.8.

- **Total maintenance rituximab dose (mg)** – cumulative rituximab dose across the maintenance phase of treatment only, from the Treatment Form of months 4, 8, 12, 16 and 20. Missing data (due to early withdrawal or any other reason –e.g. missing form) will be ignored (i.e. it's assumed no treatment was given, 0 mg).
- **Overall full rituximab treatment – maintenance (Yes/No)** – categorical variable, determining whether the subject has received all five full rituximab infusions as per protocol. Subjects are assumed to have followed protocol unless deviations were explicitly recorded in the Treatment form (i.e. "Treat6" = 1), any recorded deviation is considered an overall non-compliance, while missing forms are ignored.
- **Number of full rituximab infusions administered (integer)** – calculated across the maintenance phase of treatment, from the Treatment form of month 4,8,12,16 and 20. Counts explicitly the number of months when rituximab treatment was administered according to protocol. Thus "3 doses" would mean that 3 infusions administered were given as per protocol. Missing forms (NA) are ignored.
- **Total maintenance IV methylpredniso(lo)ne dose (mg)** – cumulative IV methylpredniso(lo)ne dose across the maintenance phase of treatment only, from the Treatment form. Missing data (due to early withdrawal or any other reason –e.g. missing form) will be ignored (i.e. it's assumed no treatment was give, 0 mg).

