#### 6. Treatment exposure (Follow Up Form)

- **Average predniso(lo)ne dose (mg/day)** – average predniso(lo)ne dose, from randomisation to the end of trial, using the most recent daily dose as recorded in the Follow Up form at month 4, 8, 12, 16, 20, 24, 27, 30, 36, 42, and 48. If predniso(lo)ne treatment was explicitly recorded as not given in the Follow Up Form (i.e. FUp1a1 = "No") then a dose = 0 mg/day will be implied, while missing data (due to early withdrawal or any other reason –e.g. missing form) will be ignored.

---

 A separate variable in the Follow Up form reports cumulative rituximab dose at 24 months, which includes doses administered during the induction phase.

 A separate variable in the Follow Up form reports cumulative IV methylpredniso(lo)ne dose at 24 months, which includes doses administered during the induction phase

- **Average predniso(lo)ne dose (mg/day) in the maintenance phase** – as above but calculated using the most recent daily dose as recorded in the Follow Up form at month 4, 8, 12, 16, 20, and 24 only.
- **AUC of predniso(lo)ne dose (mg)** – Area under the curve of predniso(lo)ne dose, calculated using the most recent daily dose as recorded in the Follow Up form at month 4, 8, 12, 16, 20, 24, 27, 30, 36, 42, and 48 employing a vertical step function and assuming a month to be 30 days. Missing data will be assumed to have a value of 0 mg/day.
- **AUC of predniso(lo)ne dose (mg) in the maintenance phase** – as above but calculated using the most recent daily dose as recorded in the Follow Up form at month 4, 8, 12, 16, 20, and 24 only.
- **Average azathioprine dose (mg/day)** – average azathioprine dose, from randomisation to the end of trial, using the most recent daily dose as recorded in the Follow Up form at month 4, 8, 12, 16, 20, 24, 27, 30, 36, 42, and 48. Missing data (due to early withdrawal or any other reason – e.g. missing form) will be ignored.
- **Average azathioprine dose (mg/day) in the maintenance phase** – as above but calculated using the most recent daily dose as recorded in the Follow Up form at month 4, 8, 12, 16, 20, and 24 only.
- **Average methotrexate dose (mg/week)** – average methotrexate dose, from randomisation to the end of trial, using the most recent daily dose as recorded in the Follow Up form at month 4, 8, 12, 16, 20, 24, 27, 30, 36, 42, and 48. Missing data (due to early withdrawal or any other reason –e.g. missing form) will be ignored.

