### 9.10.2 Glucocorticoid treatment

Concomitant glucocorticoid (GC) treatment in the maintenance phase was permitted as follows. A GC dose of 10 mg/day or less is a requirement for randomisation. GC reduces to 5 mg/day by month 6, according to schedule 2 (Table 7), and continues at 5 mg daily until month 16. GC dose is then reduced to 2.5mg/day and completely withdrawn at month 20.

---

 From randomisation to month 24 from enrolment inclusive.

 As recorded in the Follow Up form at month 24, it includes induction phase doses.

Table 7: CG Schedule 2

	Maintenance Schedule Daily Prednisolone dose (mg)
Week	
12	10
14	10
16 (randomisation)	10
18	7.5
20	7.5
22	5
24	5

Alternate day dosing regimens (i.e. those that use two different doses on alternate days) may be used to achieve the appropriate average daily dose required by the protocol but differences in alternative day doses may not be greater than 5 mg. For example, a dose of 7.5 mg/day may be achieved by alternating daily doses of 10 mg/day and 5 mg/day.

For all patients follow-up daily dose of prednisolone was recorded at each visit in the maintenance phase (months 4, 8, 12, 16, 20, 24, 27, 30, 36, 42 and 48) in the Follow-Up Form. Section 1 and 2 of the form will be reported at each time point using the full analysis population. The following variables will be summarised in accordance with section 9:

- Number of patients receiving the following treatment since the last evaluation:
  - a) Predniso(lo)ne
  - b) Rituximab
  - c) Azathioprine
  - d) Methotrexate
  - e) Mycophenolate Mofetil
  - f) Pneumocystis prophylaxis
    - i) Co-trimoxazole

---

 Rituximab treatments as recorded in the Follow-Up Form. Includes rituximab received as part of protocol and outside of protocol.

- ii) Dapsone
- iii) Other
- g) Aspirin
- h) Warfarin
- Doses of the following treatments at each visit:
  - a) Predniso(lo)ne (mg/day)
  - b) Azathioprine (mg/day)
  - c) Methotrexate (mg/week)
  - d) Mycophenolate Mofetil (g/day)
- In addition, the following derived variables (details in section 9.2) will be calculated across the maintenance phase (from month 4 to month 24) and overall (from randomisation to the end of the trial):
  - a) Average predniso(lo)ne dose (mg/day)
  - b) AUC of predniso(lo)ne dose (mg/day)
  - c) Azathioprine (mg/day)
  - d) Methotrexate (mg/week)
  - e) Mycophenolate Mofetil (g/day)

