IV methylpredniso(lo)ne treatment, as recorded in the Treatment Form, will be reported at each time point using the full analysis population. The following variables will be summarised in accordance with section 9:

- IV methylpredniso(lo)ne treatment (Yes/No)
- Dose (mg)
- Cumulative IV methylpredniso(lo)ne dose (mg) up to 24 months
- Total IV methylpredniso(lo)ne dose in maintenance phase (mg) – derived variable, details in section 9.2

Reasons given for significant deviations from the GC protocol (defined as a  $\pm$  25% of the protocol specified dose, for period greater than 2 weeks) will be listed per patient, per visit in the appendix. Additionally a frequency table of the number of predniso(lo)ne deviations per patient per visit will be provided.

A count of the number of patients whose dose of azathioprine, methotrexate, or mycophenolate was changed will be reported per visit, and overall. Details (date of dose change, clinical side effects/intolerances, laboratory abnormalities, other

reasons) as recorded in Section 2 of the form will be listed per patient per visit in the appendix.

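### Secondary endpoint 5 (cumulative glucocorticoid exposure): the prednisolone AUC scores missing doses as 0 mg/day, and no combined total adds the IV methylprednisolone that protocol maintenance schedules only in the rituximab arm

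*SAP*

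**What the plan says.** SAP 5.2.2 lists "Cumulative GC exposure" as secondary endpoint 5, as does Protocol 9.6.2. SAP 5.2 says that the endpoints are described in sections 9 to 12, but no variable there is tied to endpoint 5. The relevant variables are in SAP 9.2 and are reported under SAP 9.10.2:

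- **Prednisolone AUC.** It uses the daily dose on the Follow Up form, "employing a vertical step function and assuming a month to be 30 days". Its rule for gaps is "Missing data will be assumed to have a value of 0 mg/day". Table 6 gives the oral dose field as its only source.
- **Average prednisolone dose.** It uses the same form. Where the form records that none was given, "then a dose = 0 mg/day will be implied, while missing data" are ignored.
- **Total maintenance IV methylprednisolone.** It is a separate sum from the Treatment form. A missing entry is handled as "assumed no treatment was give, 0 mg".

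Protocol 13.2 states that "100 mg IV methylprednisolone will be administered prior to each maintenance dose", and Protocol 11.1.1 says the same. The maintenance doses are at months 4, 8, 12, 16 and 20. The control arm takes oral drugs (Protocol 11.2 to 11.4) with no scheduled IV steroid.

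**The concern.** There are two separate problems.

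1. **Zero fill.** A dose that was not recorded is treated as a dose that was not taken. For a background drug taken every day until month 20, that understates anyone with an absent form or an early exit. It also conflicts with the average-dose rule, so two summaries of one drug respond in opposite ways to the same gap.
2. **Oral only.** Both documents treat IV methylprednisolone as a glucocorticoid (Protocol 11.5.1; SAP 9.10.2). The AUC omits it, and by design the omitted amount falls in one arm. Read as endpoint 5, the AUC understates exposure on rituximab even with complete data.

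A smaller problem is that the direction of the step function is not stated, so the AUC cannot be reproduced from the text.

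The protocol motivates the trial partly by toxicity from cumulative glucocorticoid exposure (Protocol 7.1), so readers will look at this comparison.

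**Working it through.** The documents give no figure for cumulative exposure to reproduce. The sizes below come from the protocol schedule with the SAP's 30-day month, taking week 16 as month 4.

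**Scheduled oral dose, months 4-24** (Protocol 11.5.1 and Schedule 2)

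- 14 days at 10 mg, 28 at 7.5 mg, 318 at 5 mg, 120 at 2.5 mg, then 0.
- 140 + 210 + 1,590 + 300 = 2,240 mg, the same in both arms.
- Other calendar conventions give 2,280 to 2,319 mg, which leaves the percentages below almost unchanged.

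**IV dose left out of the AUC**

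- 5 x 100 = 500 mg on rituximab, 0 mg scheduled on control.
- 500 / 2,240 = 22%. At an assumed factor of 1.25, 625 / 2,240 = 28%. The documents give no factor.
- Combined total for a compliant patient: 2,740 to 2,865 mg on rituximab against 2,240 mg on azathioprine.

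**Step direction.** Visits at months 4, 8, 12, 16, 20 and 24 are 120 days apart. The SAP does not say whether the month-16 and month-20 forms hold the dose before or after that visit's reduction, so both are shown.

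| Recorded dose | Visit doses (mg/day) | Forward | Backward |
|---|---|---|---|
| Before change | 10, 5, 5, 5, 2.5, 0 | 27.5 x 120 = 3,300 | 17.5 x 120 = 2,100 |
| After change | 10, 5, 5, 2.5, 0, 0 | 22.5 x 120 = 2,700 | 12.5 x 120 = 1,500 |

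Forward carries a dose to the next visit; backward applies it to the interval just ended. Against 2,240 mg the range is -33% to +47%, identical in both arms for compliant patients.

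**Zero fill, one absent form.** Month 8 or month 12: 5 x 120 = 600 mg lost. If the unrecorded dose was 20 mg/day for a relapse, the AUC loses 20 x 120 = 2,400 mg.

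**Zero fill, early exit.** Loss by last form received (the same in either direction):

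| Last form | Before change | After change |
|---|---|---|
| Month 4 | 2,100 | 1,500 |
| Month 8 | 1,500 | 900 |
| Month 12 | 900 | 300 |
| Month 16 | 300 | 0 |
| Month 20 | 0 | 0 |
| Mean | 960 | 540 |

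At the planned 5% drop-out (Protocol 16.3), with exits spread evenly over these visits and doses on schedule, the mean loss per patient is 0.05 x 960 = 48 mg or 0.05 x 540 = 27 mg.

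**The two oral summaries side by side.** For a patient whose last form is month 8, the AUC falls to 1,800 mg (forward) or 600 mg (backward). The average dose rises to (10 + 5) / 2 = 7.5 mg/day, from 27.5 / 6 = 4.58 or 22.5 / 6 = 3.75 with all forms present.

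**The case against.** The strongest reply is that the report will already hold every component. SAP 9 and 9.10.2 summarise average oral dose, oral AUC and IV methylprednisolone by arm, and the average-dose variable already avoids zero fill. SAP 8.5 expects few missing data, and SAP 6.4 says that missing forms are routinely queried. No formal test of glucocorticoid exposure is planned; SAP 10.2 covers relapse outcomes only.

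Most of this stands, and it limits the weight of the point. A reader might infer that the IV steroid is hidden. It is not: it has its own table. What remains is that readers must choose a conversion and do the sum themselves, and that comparing arms on mean doses would not give the combined distribution.

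A reader might also infer that zero fill biases the comparison between arms. The documents do not support that, since they show no arm difference in missing forms.

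Nor can the IV omission be said always to outweigh zero fill. With evenly spread exits on scheduled doses, early exit would have to differ by 500 / 960 = 52 percentage points between arms to match 500 mg. If the last form is month 8 the figure is 500 / 1,500 = 33 points, and if month 4 it is 500 / 2,100 = 24 points. Relapse doses would lower it further.

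The unit slip (mg in SAP 9.2 and Table 6, mg/day in SAP 9.10.2) is minor. So is the SAP's silence on whether visits after the common close count as missing in the overall AUC: the scheduled dose is 0 by then.

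**Conclusion.** The point holds for the definition of a descriptive secondary endpoint. The AUC treats unrecorded doses as not taken, against the SAP's own rule for the average dose. It also omits 500 mg of IV methylprednisolone scheduled in one arm, which is 22-28% of the scheduled oral dose over months 4-24. The IV gap needs no missing data. It assumes that infusions are given as planned and a factor of 1.0 to 1.25. Control patients may receive IV steroid for a relapse under local practice (Protocol 11.6), which would narrow the gap by an amount the documents do not give.

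Zero fill can cost an individual 600 mg or more, but its expected effect on the mean is small: 27-48 mg under the stated drop-out assumptions. The step direction matters for reproducibility and for the absolute level, not for the difference between compliant patients.

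None of this touches the primary analysis, and it would be wrong to read it as doing so.

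**What to change.** In SAP 9.2 and 9.10.2:

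- Define endpoint 5 as oral plus IV dose in prednisone equivalents. Show both components by arm, state the conversion factor, and vary it over 1.0 to 1.25.
- Score 0 only where the form records that the drug was not given, or where no form was due. SAP 9.10.1 describes the Treatment form as a record of rituximab treatment, so control patients may have none due.
- Fill a gap between two recorded visits from the adjacent recorded doses. An arm average would give a patient with a relapse a typical dose.
- After exit or common close, count exposure to last follow-up and show observed time beside it.
- Report months 4-24 and the overall period. Neither document gives the endpoint a window, so restricting it to one would redefine it.
- Keep zero fill as a sensitivity analysis.
- State the step direction, and give the unit as mg throughout.

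The cost is SAP wording and a little programming, with no new data. The downside is an assumed conversion factor and a simple gap rule, which can miss a short steroid course between visits.

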#### 7. Clinical Laboratory Evaluations

- **ANCA status (Positive Both/anti-PR3/anti-MPO, Negative, Unknown)** – a categorical variable, calculated from variables in the Clinical Laboratory Test Form recording ANCA positivity (anti-PR3 and anti-MPO) at each visit. Calculated according to the following rules:

**Table 5: ANCA Status**

		Anti-MPO		
		Positive	Negative	Not measured
Anti-PR3	Positive	Positive PR3 & MPO	Positive PR3	Positive PR3
	Negative	Positive MPO	Negative	Unknown
	Not measured	Positive MPO	Unknown	Unknown

Table 6: Details of formulas for derived variables

Variable name	Label	Type	Original variables (MACRO ShortCode)	Formula
MHDuration	Prior disease duration	Real	MHDat1, Visit1	Date difference (years)
HisANCA	Historical ANCA positivity	Category	MHEli1, MHEli2	See Table 4 for details
BLM_Score BLM_Score_cat	Total number of Body Systems affected	Integer/ Category	BLM_* variables	Sum
MHCycl	Total cyclophosphamide	Category	MHTre3, MHTre4	if either = 1 then => 1 (Yes) else => 0 (No)
MHCyclDose	Cumulative cyclophosphamide dose	Real	MHCyc1, MHIVC1	Sum
MHRitCyc	Previous treatment with rituximab or cyclophosphamide (either IV or oral)	Category	MHTre5, MHCycl	if either = 1 then => 1 (Yes) else => 0 (No)
MHImmN MHImmN_cat	Number of prior immunosuppressants	Integer/ Category	CumCyclo, MHTre5, MHTre6, MHTre7, MHTre8, MHTre11, MHTre12, MHImS1, MHImS2, MHImS3, MHImS4, MHImS5, MHImS6	Sum
BVASStatus	Disease status	Category	BVAS12a, BVAS12b, BVAS12c, BVAS12d	Hierarchical order, categories evaluated in order, from the most specific to the most general: 1. Remission 2. Severe flare 3. Limited flare 4. Persistent
CDAScore CDAScore_cat CDAScore_grp	Total CDA score	Integer/ Category	selected variables of CDA Form (see section 9.8)	Sum
CDADiff CDADiff_cat	Change in total CDA score between month 4 and month 12, month 24, month 36 & month 48. Change in total CDA score between	Integer/ Category	CDAScore	Difference

	month 24 and month 36 & month 48			
TreatRituxSum	Total rituximab dose (mg)	Real	TreatTotalRitux	Sum
TreatRituxPrctcol	Overall full rituximab treatment	Category	TreatAdmnProtcol	Yes if sum(TreatAdminProtocol="Yes")=5
TreatRituxMonths	Number of full rituximab infusions	Integer/Category	TreatAdmnProtcol	count(TreatAdminProtocol="Yes")
TreatMPredDose	Total IV methylpredniso(lo)ne dose (mg)	Real	TreatMPredDose	Sum
PredMean PredMean24	Average predniso(lo)ne dose (mg/day) - (Overall /Maintenance)	Real	FUp1aPredDose	Average If FUp1a1 then Fu1aPredDose=0
PredAUC PredAUC24	AUC of predniso(lo)ne dose (mg) - (Overall /Maintenance)	Real	FUp1aPredDose	Vertical step function, assumes month=30days
AZAMean AZAMean24	Average azathioprine dose (mg/day) - (Overall /Maintenance)	Real	FUp1cAzathiDose	Average
MTXMean MTXMean24	Average methotrexate dose (mg/week) - (Overall /Maintenance)	Real	FUp1dMTXDose	Average
MMFMean MMFMean24	Average mycophenolate mofetil dose dose (mg/week) - (Overall /Maintenance)	Real	FUp1eMMFDose	Average
N.Month N.overall N.maint	Number of oral immunosuppressants	integer	Azathioprn follwup FUp1dMTX FUp1eMMF	group by subject & month
ANCA	ANCA Status	Category	CLAnt5 & CLAnt7 CLAnt9 & CLAnt11 CLAnt13 & CLAnt15 CLAnt1_2 & CLAnt3_2	See Table 5 for details

### 9.3 Protocol Deviations

Protocol deviations in the administration of treatments (rituximab and GCs) are detailed in section 9.9.

### 9.4 Demographic and Baseline Variables

Demographic details and subject characteristics, as specified in the Enrolment and Baseline Medical History Forms (Demography section), will be recorded at the screening visit and entered in the MACRO database.

The following demographic and baseline variables will be summarised in accordance with section 9 using the full analysis population. Frequency tables will be presented by treatment allocation (“Azathioprine”, “Rituximab”) and further subdivided by induction regimen at enrolment (“1A”, “1B”).

#### 9.4.1 Demographics

- Age (years), coarsening into ranges:
  - Under 18
  - 18–64
  - 65–85
  - Above 85
- Sex (M/F)
- Race (White/Black/Asian/Hispanic/Other)
- Weight (kg), converting from imperial units if necessary (1 lb = 2.205 Kg) and rounding to 1 decimal figure
- Height (cm), converting from imperial units if necessary (1 inch = 2.54 cm) and rounding to 1 decimal figure

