### 10.3 Enrolment and Assignment and Trial Number

The patient will be allocated a unique trial identification number to be used on all trial related material for the patient upon enrolment. Patients will be enrolled by logging into an internet based website (TENALEA) provided by the Cambridge Clinical Trials Unit. After logging in, the investigator will confirm eligibility criteria, ANCA subtype, relapse severity and the prednisolone induction regimen followed (1A or 1B). Investigators are required to enter the height and weight of the patient. Body surface area and the dose for each of the 4 rituximab induction infusions ( $375\text{mg}/\text{m}^2$ ) will be automatically calculated within TENALEA using the Dubois and Dubois formula (17). A target date for randomisation four months in the future will be generated. This information should be recorded on the enrolment CRF page.

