## 8.8 Multi-centre Studies

(ICH E3; 9.7.1, 11.4.2.4. ICH E9; 3.2)

RITAZAREM is a joint venture of the European Vasculitis Study Group (EUVAS) and the Vasculitis Clinical Research Consortium (VCRC). RITAZAREM will occur in multiple centres internationally including Europe, North America and Australia/New Zealand. Plans are for approximately 50–60 centres to recruit patients.

Data is recorded in a single MACRO database across all study centres. Study centre will form part of the information recorded, so that it can be identified during the statistical analysis. Recruitment and patient's retention rate will be reported by site and grouped by country.

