#### 9.4.3 Stratification variables

---

 Calculated using the Du Bois formula (14)

The Enrolment Form records the stratification variables at baseline (Month 0): prednisolone induction regimen, ANCA type, and relapse severity. The following frequency tables will be summarised in accordance with section 9:

- Relapse severity (Severe/Non-severe) stratified by prednisolone regimen (1A/1B).
- ANCA type (anti-PR3/anti-MPO) stratified by prednisolone regimen (1A/1B).
- Relapse severity (Severe/Non-severe) stratified by ANCA type (anti-PR3/anti-MPO).

Corresponding mosaic plots will also be produced.

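### SAP 9.4.1 states the pound-to-kilogram conversion the wrong way round; applied as written, it would overstate each weight recorded in pounds 4.86-fold in the baseline table

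*SAP*

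**What the plan says.** SAP 9.4.1 (Demographics) lists the variables for the baseline table. The weight entry reads "Weight (kg), converting from imperial units if necessary", and the bracket that follows gives the factor: "converting from imperial units if necessary (1 lb = 2.205 Kg"). The result is rounded to one decimal. The height entry just below has the same layout, "converting from imperial units if necessary (1 inch = 2.54 cm").

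SAP 9.4 sets the use of these variables: "The following demographic and baseline variables will be summarised in accordance with section 9 using the full analysis population". Tables are split by treatment allocation and by induction regimen. SAP section 9 asks for the mean, standard deviation, median, minimum and maximum of each continuous variable.

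No other place in the protocol or SAP gives a pound-to-kilogram factor. SAP Table 8 holds conversion factors for laboratory units only.

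**The concern.** The equation is false as printed, and it is the only instruction the SAP gives for turning pounds into kilograms. It is hard to dismiss as loose shorthand. The height line beside it puts the imperial unit on the left and the metric equivalent on the right, is correct, and is applied by multiplying. The factors in Table 8 are also described as multiplicative. A programmer who reads the weight line in the same way would multiply pounds by 2.205.

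The SAP itself foresees imperial entries, and SAP 8.8 says "RITAZAREM will occur in multiple centres internationally including Europe, North America and Australia/New Zealand", so weights in pounds are plausible. At stake is the accuracy of one baseline characteristic in a table that readers use to judge who was enrolled and whether the arms are comparable. The range limits in SAP Table 9 apply to laboratory tests and would not catch a bad weight. SAP section 15 requires an explicit check of the efficacy code and leaves checks of other code to the reviewing statistician's discretion.

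**Working it through.** **Inputs**

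- Stated factor: 2.205, printed as kilograms per pound (SAP 9.4.1).
- Definition of the pound: 1 lb = 0.45359237 kg.
- Share of weights recorded in pounds: not in the documents. Assumed range 10% to 30%.
- True mean weight: not in the documents. 75 kg is used for illustration only; the percentage changes do not depend on it.

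**Step 1: reproduce the stated figure.** 1 / 0.45359237 = 2.20462, which rounds to 2.205. The number is right as pounds per kilogram. As kilograms per pound the value should be 0.4536 (1 / 2.205 = 0.4535). So the digits are correct and the units are swapped.

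**Step 2: size of the error for one patient.** Literal use gives lb × 2.205; correct use gives lb × 0.45359237. The ratio is 2.205 / 0.45359237 = 4.861, the same at every weight (2.205² = 4.862 if the rounded factor is used both ways).

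| Recorded (lb) | As written (kg) | Correct (kg) |
|---|---|---|
| 110 | 242.6 | 49.9 |
| 154 | 339.6 | 69.9 |
| 180 | 396.9 | 81.6 |
| 220 | 485.1 | 99.8 |

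**Step 3: effect on a group mean.** Let s be the share recorded in pounds, and assume those patients have the same true mean weight as the rest. Then

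reported mean / true mean = (1 − s) + 4.861 s = 1 + 3.861 s.

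| s (assumed) | Ratio | Rise in mean | Mean if true mean is 75 kg |
|---|---|---|---|
| 10% | 1.386 | 39% | 104 kg |
| 20% | 1.772 | 77% | 133 kg |
| 30% | 2.158 | 116% | 162 kg |

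If no weight was recorded in pounds, the ratio is 1 and the line has no effect.

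**Step 4: where weight enters the analysis.** The Cox model is adjusted for ANCA type, relapse severity and prednisone induction regimen (SAP 8.4 and 10.1). Weight is not among these covariates, is not a randomisation stratum (SAP 6.3), and is not a listed predictor in the hypogammaglobulinaemia regression (SAP 11.3). Its listed use is in the descriptive baseline table.

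**The case against.** The case for leaving this alone has four parts.

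- *A bracketed equation is not code.* The programmer may well have divided. This stands: the documents do not include the code, so they cannot show that any weight was misreported. It limits the claim to what happens if the text is followed; it does not make the text right.
- *Few weights, or none, may be in pounds.* Azathioprine is dosed per kilogram (protocol 11.2) and the glucocorticoid schedules use weight in kilograms (protocol 11.5.1), so sites needed weight in kilograms anyway, and the SAP provides for conversion only where needed. This also stands, and is why a range is shown and not a single figure.
- *The error would be seen.* The maximum is tabulated, and a value near 400 kg would stand out. That is probably true, but it relies on someone noticing a bad result instead of on a correct rule.
- *Nothing important depends on it.* This stands for the efficacy analysis and for the safety regression.

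A reader might go further and infer that body surface area, and with it the induction dose, is wrong. The documents do not support that. Protocol 10.3 has the investigator enter height and weight at enrolment, after which body surface area and dose "will be automatically calculated within TENALEA using the Dubois and Dubois formula (17"). That happens in the enrolment system, not through the SAP's conversion. SAP 9.4.2 lists body surface area among the enrolment characteristics, and its footnote says only "Calculated using the Du Bois formula (14"). The footnote names a formula; it does not say that the value is recalculated from the converted weight, and so it is not a second place where the error occurs.

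**Conclusion.** The stated rule is wrong, and the point is minor. SAP 9.4.1 inverts the conversion, and literal use would overstate each weight recorded in pounds 4.86-fold. That factor follows from unit arithmetic alone.

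The effect on the baseline table rests on three conditions that the documents leave open: that some weights were recorded in pounds, that the code follows the text, and, for the 39% to 116% range, that the share in pounds is 10% to 30% with equal true mean weights.

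The documents do not support the inference that reported weights are in fact wrong, that dosing or the enrolment body surface area is affected, or that any efficacy result would change.

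**What to change.** In SAP 9.4.1, replace the bracketed equation with `1 kg = 2.205 lb (kg = lb / 2.205)`. Check that the code producing the weight table uses this direction, and correct it only if it does not.

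The cost is one line of text and a brief look at the code. Nothing changes in the design, the data collected or the primary analysis.
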